13.3 Serious Adverse Event Criteria and Reporting Procedures

13.3.1 Definitions

A serious adverse event (SAE) is defined as one which:

- Constitutes a congenital anomaly/birth defect
- Results in persistent or significant disability/incapacity
- Requires inpatient hospitalization or prolongation of existing hospitalization, unless hospitalization is for:
 - Routine treatment or monitoring of the studied indication, not associated with any deterioration in condition
 - Elective or pre-planned treatment for a pre-existing condition that is unrelated to the indication under study and has not worsened since signing the informed consent
 - Treatment on an emergency outpatient basis for an event not fulfilling any of the definitions of an SAE given above and not resulting in hospital admission
 - Social reasons and respite care in the absence of any deterioration in the patient's general condition
- Is fatal or life-threatening
- Is medically significant i.e. defined as an event that jeopardizes the patient or may require medical or surgical intervention to prevent one of the outcomes listed above

Adverse events that are grade 1-2 and expected should be reported through the RDCRN database within 20 working days and logged appropriately. Determination of causality and relatedness should be made by the site PI.

Adverse events that are grade 1-2 and unexpected should be reported through the RDCRN database within 24 hours, to local IRBs, and to the sponsor only if the event suggests that there are greater risks to study subjects than previously suspected.

Adverse events that are grade 3-4 should be considered serious if they fit into one of the categories listed above (as defined by the FDA). If the event is classified as an SAE then the appropriate reporting guidelines must be followed. All SAEs will be further classified as serious adverse events or serious adverse drug reactions based on the events relation to the study drug. For SAEs, the final determination of causality is made by the Medical Review Officer. If the event is unrelated to the drug (probably not related or definitely not related) then it is defined as a Serious Adverse Event. If the event is related to the drug (definitely related, probably related, or possibly related) then it is defined as a serious adverse drug reaction.

The principal investigator has the obligation to report all serious adverse events to the FDA, IRB, RDCRN, and Novartis Pharmaceuticals Drug Safety and Epidemiology Department (DS&E).

All SAEs deemed reportable by the medical review officer, will be submitted to the FDA by the investigator utilizing the Form FDA 3500A (MedWatch Form).

13.3.2 Adverse Event Reporting

All adverse events will be recorded in the RDCRN database for reporting to respective IRBs, FDA, industry sponsors, and for data analysis. The DSC will review all AEs at regularly scheduled meetings.

- Within 24 hours (of learning of the event), investigators must report any reportable Serious Adverse Event (SAE) that:
 - Is considered life-threatening/disabling or results in death of subject -OR-
 - Is Unexpected/Unanticipated
- Investigators must report all other reportable SAEs to the RDCRN database within 5 working days (of learning of the event)
- All other (suspected) reportable AEs must be reported to the RDCRN within 20 working days of the notification of the event or of the site becoming aware of the event.

To ensure patient safety, every SAE, regardless of suspected causality, occurring after the patient has provided informed consent and until at least 28 days after the patient has stopped study treatment/participation, after protocol-specified procedures begin (e.g., placebo run-in, washout period, double-blind treatment, etc.) and 28 days after the patient has stopped study treatment, after the start of any period in which the study protocol interferes with the standard medical treatment given to a patient (e.g., treatment withdrawal during washout period, change in treatment to a fixed dose of concomitant medication) and until 28 days after the patient has stopped study treatment.

All SAEs must be reported to Novartis within 24 hours of learning of its occurrence. Information about all SAEs is collected and recorded on the Serious Adverse Event Report Form; all applicable sections of the form must be completed in order to provide a clinically thorough report. The investigator must assess and record the relationship of each SAE to each specific study treatment (if there is more than one study treatment), complete the SAE Report Form in English, and send the completed, signed form by fax to ([contact]) within 24 hours to the oncology Novartis DS&E department. Should the designated SAE Fax number be nonfunctional please send SAEs to the designated SAE mailbox: [contact]. A Novartis SAE Coversheet must be attached to all SAE Submissions. This includes serious, related, not related, labeled (expected) and, unlabeled (unexpected) adverse experiences. All deaths during treatment or within 30 days following completion of active protocol therapy must be reported within24 hours.

Any SAEs experienced after this 28 days period should only be reported to Novartis if the investigator suspects a causal relationship to the study drug. Recurrent episodes, complications, or progression of the initial SAE must be reported as follow-up to the original episode within 24 hours of the investigator receiving the follow-up information. A SAE occurring at a different time interval or otherwise considered completely unrelated to a previously reported one should be reported separately as a new event. The end date of the first event must be provided.

The original copy of the SAE Report and the fax confirmation sheet must be kept within the Trial Master File at the study site.

Follow-up information is sent to the same fax number as the original SAE Report Form was sent, using a new fax cover sheet, stating that this is a follow-up to the previously reported SAE, and giving the date of the original report. Each re-occurrence, complication, or progression of the original event should be reported as a follow-up to that event regardless of when it occurs. The follow-up information should describe whether the event has resolved or continues, if and how it was treated, whether the blind was broken or not (if applicable), and whether the patient continued or withdrew from study participation.

If the SAE is not previously documented in the Everolimus Investigator Brochure or Package Insert (new occurrence) and is thought to be related to the Novartis study drug, a DS&E associate may urgently require further information from the investigator for Health Authority reporting. Novartis may need to issue an Investigator Notification (IN), to inform all investigators involved in any study with the same drug that this SAE has been reported. Suspected Unexpected Serious Adverse Reactions (SUSARs) will be collected and reported to the competent authorities and relevant ethics committees in accordance with Directive 2001/20/EC or as per national regulatory requirements in participating countries.

13.4 Adverse Event Data Management

Upon entry of a serious adverse event, the DMCC created Adverse Event Data Management Form will immediately notify the Study Chair, site PIs, the Medical Review Officer, and any additional agencies (if applicable - industry sponsor, CTEP, etc.) of any reported adverse events via email.

Serious adverse events: The site physician will determine initial causality (definitely not related, probably not related, possibly related, probably related, definitely related) of the adverse event when submitting the report in the DMCC database. The final determination of causality will be made by the study appointed medical monitor, [name].. The medical monitor [and, if applicable, sponsor] may request further information if necessary and possibly request changes to the protocol or consent form as a consequence of the adverse event. A back-up notification system is in place so that any delays in review by the medical monitor beyond a specified period of time are forwarded to a secondary reviewer. The Adverse Event Data Management Form maintains audit trails and stores data (and data updated) and communication related to any adverse event in the study.

Non-serious expected adverse events: Except those listed above as immediately reportable, non-serious expected adverse events that are reported to or observed by the investigator or a member of his/her research team will be submitted to the DMCC in a timely fashion (within 20 working days). The events will be presented in tabular form and given to the medical monitor and Safety Monitoring Committee on a bi-annual basis. Local site investigators are also required to fulfill all reporting requirements of their local institutions.

The DMCC will post aggregate reports of all reported adverse events for site investigators and IRBs.

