The average starting dose will be 4.5 mg/m²/day of trial therapy (either everolimus or placebo), rounded to the nearest 2.5mg dose. The BSA should be calculated (section 7.15) based on an accurate height and weight measurement performed according to institutional guidelines. Leftover study medication, as well as all used blister packs, should be collected at each study visit, and drug should be accounted for at this time. If 2.5mg tablets become unavailable during the trial, patients prescribed a dose including 2.5mg tablets will be instructed to alternate between a higher and lower dose. The site physician will instruct the patient to take the higher dose on Monday, Wednesday, and Friday. The patient will take the lower dose on Tuesday, Thursday, Saturday, and Sunday. For example, a patient prescribed a dose of 7.5mg will take 10mg on Monday, Wednesday, and Friday, and 5mg on Tuesday, Thursday, Saturday, and Sunday.

A maximum volume of 3 ml of blood will be drawn for trough everolimus PK levels when necessary. The blood draws will be timed to occur at 24 ± 4 hours after ingestion of the drug. Blood collection for PK samples may be conducted during a scheduled visit on-site or via a designated and trained remote healthcare service. Everolimus levels will be measured at ARUP laboratories in Salt Lake City, UT, in conjunction with LabConnect, LLC. When necessary, a kit for remote collection of blood samples can be sent to the participant and returned per the shipping instruction by express mail.

Dose adjustments in the blinded phase of the trial can occur in both placebo (randomized modification) and active (based on PK findings) arms and will be at the discretion of a central unblinded investigator, [name]. or back-up unblinded investigator, [name]. In the event both Drs. [name] and [name] are unavailable, [name], Medical Review Officer, will serve as the unblinded investigator for the purposes of PK-driven dose adjustments. An unblinded research nurse will assist the unblinded physicians and the Medical Review Officer in their roles and will make sure that communications between them and the different sites is occurring in a timely manner.

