Dose adjustments will be permitted, based on safety findings and PK levels. The site PI will initiate any safety level related dose adjustments according to the protocol, in collaboration with the Medical Review Officer as appropriate. PK based dose adjustments will be initiated by the unblinded physician. All dose adjustments will be made using the 2.5mg tablets (i.e. increase by 2.5mg, decrease by 2.5mg, or maintain dose). If a dose adjustment is made for safety purposes, the unblinded physicians and Medical Review Officer should be made aware of any dose modifications as soon as possible.

Sites may substitute 5mg tablets (or 10mg tablets in open label) for 2.5mg tablets where necessary, as long as the single dose level increase or decrease is maintained. For example, an adjustment from 7.5mg to 10mg can be made by prescribing two 5mg tablets (or one 10mg tablet in open label) rather than one 5mg and two 2.5mg tablets. Following a dose adjustment, sites can mail the extra 5mg tablets to the participant in between visits to make up for the remaining days until the next site visit. One level dose increase would be increasing the dose by 2.5mg and a one level dose decrease would be decreasing the dose by 2.5mg as stated above.

Placebo Arm: Placebo dose adjustment procedures are defined in the unblinded dose adjustment protocol – accessible only to the unblinded physician(s) and the DMCC. The site team will be blinded with respect to treatment assignment at all times. [name], [name], and [name] will receive instructions regarding dose modifications for participants on placebo from the DMCC. When PK values become available for individuals in placebo arm, [name] or [name] will refer to the provided instructions and notify site Pl/coordinator of dose status (increase, decrease, or maintain) for individuals assigned to a dose adjustment.

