7.5 Randomization Procedure

Subjects will be randomized 1:1 to everolimus or placebo after meeting all eligibility criteria. A designated member of the research team will communicate to the participant that randomization has occurred and sufficient study drug will be dispensed to cover the interval until the next study visit. This is a double-blind study. The study design allows patient unblinding during the double-blind phase only in very precise circumstances (section 7.6.1).

Randomization data are to be kept strictly confidential until the time of unblinding at discontinuation or at the time of final analysis. These data will not be accessible to anyone involved in the conduct of the study with the exception of the unblinded physicians, the Medical Monitor, the Data Safety and Monitoring Committee (DSMC), and the Data Management Coordinating Center (DMCC). The DSMC will review safety data as outlined in section 15. The identity of treatment arms will be concealed by the use of study drugs (everolimus and matching placebo) that are identical in packaging, labeling, schedule of administration and in appearance.

Prior to Baseline (Visit 2), the investigator or his/her designee will log onto the data system to verify that the patient fulfills all eligibility criteria and randomize the patient to a treatment arm. The system will assign a randomization arm, as described in the 7904 Manual of Procedures. The pharmacy will be responsible for dispensing the active drug or placebo based on the procedures outlined in the 7904 Pharmacy Manual of Procedures. The randomization will be stratified by age. Age will be stratified by two levels. Level 1 will be participants aged 5-21 years old, and level 2 will be 22-45 year olds. Permuted block sizes of two and four will be used. At the conclusion of the 6-month double-blind phase, the blind will be broken immediately. Individuals on the active drug will exit the study, and those who were on placebo will be invited to join the open label phase.

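### The role that makes the final SAE causality decision has standing access to treatment allocation, and nothing requires that decision to be recorded before allocation or drug levels are seen

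*Combined protocol and SAP*

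**What the plan says.** Two sections assign the final causality decision, under two titles. Section 13.4: "The final determination of causality will be made by the study appointed medical monitor". Section 13.3.1: "For SAEs, the final determination of causality is made by the Medical Review Officer". Section 13.3.1 then uses the decision to classify the event: if it is judged related, "then it is defined as a serious adverse drug reaction"; if not, it stays a serious adverse event. The site physician gives an initial causality rating (13.4), but that rating is not final.

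Section 7.5 withholds the randomisation data from people running the trial, "with the exception of the unblinded physicians, the Medical Monitor, the Data Safety and Monitoring Committee (DSMC), and the Data Management Coordinating Center (DMCC"). In section 6, the dose-adjustment text (listed in the contents as 6.2) adds that, when the central unblinded investigator and the back-up are both unavailable, the "Medical Review Officer, will serve as the unblinded investigator for the purposes of PK-driven dose adjustments". It also says: "An unblinded research nurse will assist the unblinded physicians and the Medical Review Officer in their roles".

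Section 15 describes an independent medical review officer who reviews adverse events and decides whether unblinding is needed.

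**The concern.** Causality is a judgement. A reviewer who knows that a patient took placebo has little room to call an event drug-related, and one who knows that the patient took everolimus may lean the other way. Blinding the causality assessment is the usual protection. Here the last word belongs to a role that is permitted to see the arm, and the protocol sets no order between seeing it and deciding.

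What is at stake is the relatedness label on SAEs. Section 2.1 names SAEs as a focus of the primary objective. Section 15 calls for aggregate reports broken down by relationship to the study drug. Section 17 predicts a between-arm difference in medication-related side effects without saying whose judgement defines that term. If a by-arm relatedness summary is produced, the plan does not prevent it from resting on a call made with the arm known.

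**Working it through.** The point concerns roles and sequence, so the main check is a cross-reading.

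1. **Who decides.** 13.4 names the medical monitor and 13.3.1 the Medical Review Officer. 13.4 also has the Medical Review Officer notified of each SAE in the same workflow. The titles therefore appear to be one role, although the documents never say so and names are removed.
2. **Can the decider know the arm?** Yes, from 7.5 and 13.4 alone, because both name the medical monitor. This step does not need the two titles to be one role.
3. **Second route to the arm.** Section 6 gives the Medical Review Officer drug-level decisions as third in line. On placebo dose changes, three people whose names are removed "will receive instructions regarding dose modifications for participants on placebo from the DMCC". By parallel with the preceding text the third is probably this officer, but that cannot be confirmed.
4. **Is there a blinding rule for the decision?** None was found in 7.5, 13.3.1, 13.4 or 15.
5. **What uses the decision?** It sets the split in 13.3.1. The primary endpoint in 2.1 is drop-out due to side effects. The tests in section 17 compare drop-out and rates of specific side effects. None of these is defined by the final SAE causality call, and a total SAE count is the same however events are attributed.

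The possible size in a relatedness summary follows from the group size. Inputs: 20 patients per arm, and the 10% difference that is to be reported as meaningful (both 17.1). Assumptions, not in the documents: the same number of patients per arm has an SAE that would be judged related under blinding, and *r* placebo patients have theirs moved to unrelated. The difference created is *r*/20:

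| *r* | Difference with no true effect |
|---|---|
| 0 | 0 points |
| 1 | 1/20 = 5 points |
| 2 | 2/20 = 10 points |
| 3 | 3/20 = 15 points |

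Two reclassified patients reach the flag. If two patients per arm had such an SAE, the summary would read 2 v 0 while total SAEs read 2 v 2. A 2 v 0 table is not statistically significant (one-sided Fisher p = C(20,2)/C(40,2) = 190/780 = 0.24), but 17.1 applies its 10% flag without requiring significance.

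**The case against.** The strongest reply is that no planned analysis uses this call. Section 17 specifies no by-arm count of serious adverse drug reactions, the related/unrelated split sits among reporting procedures, and the study describes itself as exploratory. This stands, and it limits the consequence to relatedness summaries.

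Second, section 15 has the medical review officer decide whether unblinding is required, which suggests that review starts blinded. This partly stands. It is an implication rather than a rule, and it conflicts with the standing access in 7.5. Access is also not the same as use, and the drug-level role is only third in line, so actual knowledge of an arm may be occasional.

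Third, not every SAE need reach this person: 13.4 forwards delayed reviews to a secondary reviewer and section 15 names a back-up officer. That stands, although the blinding status of neither is given.

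Fourth, the site physician's causality is already recorded, so a blinded rating exists. That is largely true, but not for every event. Under 7.6 the site obtains the assignment before the Month 6 visit or at early termination, so an SAE first assessed then, or in the 28-day follow-up, may be rated by an unblinded site.

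A reader might infer that drug-related SAE counts must differ between arms by construction, or that the primary safety comparison is compromised. The documents support neither. A difference arises only if the allocation is seen before the call is made, and the primary endpoint does not depend on the call.

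**Conclusion.** The gap is real and limited. The final SAE causality decision can be made with knowledge of the arm, so SAE relatedness, the split in 13.3.1 and any by-arm relatedness summary are open to an avoidable bias. The primary endpoint, total SAE counts and the planned tests of specific side effects are not affected. This should be fixed, but it is not a must-fix.

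The size is 5 points per reclassified patient at 20 per arm. The frequency is unknown, and the 2 v 0 example is an assumed scenario. The core conclusion rests only on 7.5 and 13.4; the added drug-level route rests on the inference that the two titles are one role.

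**What to change.** 1. In 13.3.1 and 13.4, require the final SAE causality to be recorded before any access to allocation or everolimus levels. Reconcile 7.5 with section 15 so that the monitor is unblinded only case by case, after causality is recorded. Use one title for the role. If this reviewer has acted as the unblinded drug-level investigator for a patient, send that patient's SAEs to someone who has not seen that patient's allocation or levels, such as the existing back-up or secondary reviewer, and state that person's blinding status.
2. In section 17, state that any by-arm relatedness summary uses the site physician's causality recorded before that patient was unblinded. Flag separately the SAEs first assessed after site unblinding (Month 6, early termination, 28-day follow-up), using the recorded date of unblinding.

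The cost is minor process wording and possibly the loss of the third-line drug-level back-up for some patients. The change in section 17 needs no new data collection beyond the unblinding date, because 13.4 already records the site physician's rating.

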13.5 Unanticipated Problem Reporting

The Office for Human Research Protections (OHRP) considers unanticipated problems involving risks to subjects or others to include, in general, any incident, experience, or outcome that meets all of the following criteria:

- unexpected in terms of nature, severity, or frequency given (a) the research procedures that are described in the protocol-related documents, such as the IRB-approved research protocol and informed consent document; and (b) the characteristics of the subject population being studied;
- related or possibly related to participation in the research ("possibly related" means there is a reasonable possibility that the incident, experience, or outcome may have been caused by the procedures involved in the research); and
- suggests that the research places subjects or others at a greater risk of harm (including physical, psychological, economic, or social harm) than was previously known or recognized.

Per the definition, only a subset of adverse events would be characterized as unanticipated problems. There are other types of incidents, experiences, and outcomes that are not considered adverse events, but are characterized as unanticipated problems (e.g., breach of confidentiality or other incidents involving social or economic harm).

Incidents or events that meet the OHRP criteria for unanticipated problems are to be reported to the IRB, per local institutional reporting requirements. Local institutional reporting requirements to IRBs, any GCRC oversight committee and the FDA, if appropriate, remain the responsibility of the treating physician and the Study Chair.

